9.7.1.6.9. Vital Signs

Descriptive summaries of the observed values at each scheduled visit as well as the change from baseline at each post-baseline visit will be presented.

9.7.1.6.10. Pregnancy Test

The results of pregnancy tests for women of childbearing potential will be presented in a listing.

9.7.1.7. Analysis of Other Measurements

9.7.1.7.1. Pharmacokinetic Analyses

Observed AG-73305 plasma concentrations will be summarized for each cohort for the Day 1, 24hr post-dose (if available), Week 1, and Week 4 visits. Mean plasma-concentration profiles will be graphed for each cohort.

A model-independent non-compartmental approach will be used to calculate plasma PK parameters for AG-73305, where appropriate, including AUC_{0-t} , C_{max} , and T_{max} , and summary statistics will be presented.

9.7.1.7.2. Anti-Drug Antibody Analyses

The immunogenicity (anti-AG-73305 antibody) results (reactive [positive], negative, or inconclusive) will be summarized. The titer value for positive samples will also be summarized. Quantitative relationships between immunogenicity findings and AG-73305 PK, efficacy, and/or safety variables may be explored.

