- h. IOP measurement will be performed prior to and after AG-73305 injection at Baseline/Day1. After injection, IOP will be measured within 15 minutes using a tono-pen or tono-pen like device. If IOP >30mmHg, repeat IOP measurement at 15±5 minutes post injection until pressure is reduced
- i. Color fundus photos, OCT-A and SD-OCT images will be submitted to a reading center for grading; not required for eligibility
- j. OCT-A is to be performed at baseline and at the visit (OU) when **Rescue** treatment is given. OCT-A is to be performed prior to the rescue treatment
- k. Dilated fundus exam
- l. Prednisolone acetate 1% ophthalmic suspension will be provided to patients, who will be instructed to prophylactically treat the study eye QID 2 days prior to the Baseline visit. Patients will be instructed to taper based on the Day 2 follow-up visit
- m. Within 15 minutes following intravitreal injection, a post-injection assessment will be done, including checking for count fingers or hand motion vision
- n. At selected sites, blood (~10 mL) will be collected for plasma drug monitoring on Day 1 pre-dose (all Cohorts), 1 hour (Cohort 1 and 2 only), 3 hours (all Cohorts), 8 hours (all Cohorts) and 24 hours post dose (Cohort 3 and 4 only), Week 1 (all Cohorts), and Week 4 (all Cohorts) in approximately 2-4 patients.
- o. ~20 mL of blood will be collected on Day 1 pre-dose and Weeks 1, 4, 8 and 24 from all patients for anti-drug antibody assessments.

Additional examinations and unscheduled visits can be included as safety concerns arise.

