9.5.1.5.2. Immunogenicity

Blood samples (approximately 20 mL per sample) will be collected for the assessment of anti-drug antibodies towards AG-73305 at pre-dose, Week 1, 4, 8 and 24.

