9.7.1. Statistical and Analytical Plans

General Conventions

Summary statistics for the data collected during this study will be presented to give a general description of the patients studied. Data from all sites will be combined in the computation of these descriptive summaries. Categorical variables will be summarized by the frequency and percentage of patients in each category. Continuous variables will be summarized using N, mean, standard deviation (SD), median, minimum, and maximum values.

Number of patients, minimums, and maximums will be calculated to the same number of decimal places as the source data. Means, medians, standard deviations, and quartiles will be calculated to one more decimal place than the source data. Percentages will be calculated to the nearest one decimal place. Zero count cells will be displayed as “0” with percentage of (0%). Unless otherwise noted, summaries will be performed by the treatment group and presented in the order of: AG-73305, 0.5 mg; AG-73305, 1 mg; AG-73305, 2 mg; AG-73305, 4 mg.

Baseline values will be defined as the last measurement prior to dosing of study medication. Ocular measurements will use the most recent measurement for each eye.

Numeric laboratory, pharmacokinetic, and immunogenicity data may be recorded at limits of detection (with a ‘<’ or ‘>’ sign, e.g., < 0.1 or > 0.1). To summarize laboratory data, the original value will be converted to one unit less or more at the level of measured precision (e.g. 0.4 in the case of < 0.5 and to 0.6 in the case of > 0.5). For pharmacokinetic data, for Time = 0 (predose), any result that is below the level of quantitation (BLQ) is set to zero; all other timepoints are set to missing for any computations. For immunogenicity, any titer < Value (a negative result) is set to zero. Summary tables for immunogenicity titer will not include these negative results.

The actual values will be presented in the data listings.

All data collected in this study will be presented in individual patient data listings for all patients.

Computations for all results will be performed using SAS (Version 9.4, SAS/STAT 15.2) computer software package (SAS Institute, Inc, 2013, 2020), unless otherwise specified.

Strata and Covariates

Not applicable.

Subgroups

Not applicable.

Multiplicity

Not applicable.

Missing Data and Outliers

Every attempt will be made to capture all study data. All analyses will utilize observed data only.

Visit Windows

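### The SAP does not relate post-dose anti-drug antibody results to the pre-dose sample, so a post-dose positive count can include pre-existing reactivity

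*SAP*

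**What the plan says.** The immunogenicity profile is part of the first study objective (Protocol synopsis; SAP 9.5.1). SAP 9.5.1.5.2 has blood taken "for the assessment of anti-drug antibodies towards AG-73305 at pre-dose, Week 1, 4, 8 and 24". The footnote to the protocol's schedule of activities confirms that this applies to everyone: "blood will be collected on Day 1 pre-dose and Weeks 1, 4, 8 and 24 from all patients for anti-drug antibody assessments".

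The analysis in SAP 9.7.1.7.2 has three parts:

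- Result category: "The immunogenicity (anti-AG-73305 antibody) results (reactive [positive], negative, or inconclusive) will be summarized".
- Titer: "The titer value for positive samples will also be summarized".
- An optional look at how immunogenicity relates to PK, efficacy or safety.

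The general conventions in SAP 9.7.1 set negative titers to zero and then state: "Summary tables for immunogenicity titer will not include these negative results". They also define baseline for the whole plan ("Baseline values will be defined as the last measurement prior to dosing of study medication") and promise listings ("All data collected in this study will be presented in individual patient data listings for all patients").

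Neither document, as available, defines treatment-induced or treatment-boosted ADA, a rise in titer from pre-dose, a shift from pre-dose status, or a denominator for an ADA proportion.

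**The concern.** What the objective needs to know is whether the drug provoked antibodies. That is a within-patient question: was this patient negative before and positive after, or positive before with a materially higher titer after? The planned categories and titers do not answer it.

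The rest of the SAP handles the same issue differently. Change or shift from baseline is planned for BCVA, CST, IOP, slit lamp, fundus, laboratory, ECG and vital-sign data (9.7.1.5 and 9.7.1.6). Adverse events are divided into pretreatment and treatment-emergent (9.7.1.6.1). The ADA section has no equivalent.

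The cohorts are small, so classifying one patient differently changes a cohort's proportion visibly. If the rules are left open, the rise in titer that counts, the denominator and the handling of inconclusive pre-dose results would be chosen after the results are known, in an open-label study whose data are reviewed periodically.

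**Working it through.** The plan states no ADA rate, so there is no figure of its own to reproduce. The check has four parts.

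**1. Weight of one pre-existing reactor.** SAP 9.7.2 gives cohorts of 3 to 8 and tabulates 3, 6 and 8. One patient is 1/3 = 33%, 1/6 = 17% or 1/8 = 12.5% of a cohort.

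Illustration in a cohort of 6, with one patient reactive pre-dose at an unchanged titer and one who converts: post-dose positive 2/6 = 33%; treatment-induced 1/6 = 17% of all patients, or 1/5 = 20% of those negative pre-dose.

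**2. Chance that it arises.** Let b be the share of patients reactive before dosing. It is assumed, because the documents give no value. The chance of at least one among n patients is 1 − (1 − b)^n. The same formula reproduces all 24 cells of SAP Table 2 to within 0.0005. With n = 25 for the approximate total in the synopsis:

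| b (assumed) | n = 3 | n = 6 | n = 8 | n = 25 |
|---|---|---|---|---|
| 0% | 0 | 0 | 0 | 0 |
| 2% | 0.059 | 0.114 | 0.149 | 0.397 |
| 5% | 0.143 | 0.265 | 0.337 | 0.723 |
| 10% | 0.271 | 0.469 | 0.570 | 0.928 |
| 20% | 0.488 | 0.738 | 0.832 | 0.996 |

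**3. Effect on a pooled post-dose proportion.** Let t be the induced rate among patients negative pre-dose (also assumed). Suppose pre-dose reactors stay positive without a boost. Then:

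- any post-dose positive = b + (1 − b)t
- treatment-induced, over all patients = (1 − b)t
- difference = b

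With t = 10%:

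| b (assumed) | Any post-dose positive | Treatment-induced |
|---|---|---|
| 0% | 10.0% | 10.0% |
| 2% | 11.8% | 9.8% |
| 5% | 14.5% | 9.5% |
| 10% | 19.0% | 9.0% |
| 20% | 28.0% | 8.0% |

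At b = 10% in 25 patients, that is 25 × 0.19 = 4.75 against 25 × 0.09 = 2.25 expected patients.

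**4. Whether a by-visit table would settle it.** Suppose ADA is tabulated by nominal visit, with 1/6 positive pre-dose and 1/6 at Week 4. This may be one patient with a flat titer, which is no response to drug. It may equally be one patient who reverted and another who converted. It may also be one patient whose titer rose many-fold. The category counts are identical in all three cases.

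Titers of positive samples do not fully repair this, because a converter enters the table only after dosing. With illustrative titers of 160 (unchanged) and 20 (new), the mean goes from 160 pre-dose to (160 + 20)/2 = 90 post-dose, although antibody has appeared.

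**The case against.** The strongest reply is that the information is not lost. Under the visit convention in SAP 9.7.1, summaries use nominal visits and pre-dose is a scheduled ADA timepoint, so the ordinary reading is a table with a pre-dose row. Listings of all data are promised, and with about 25 patients each course can be read individually. The titer table will also carry N, median, minimum and maximum: in the example above, N would go from 1 to 2 with a new minimum of 20, so only a reader of the mean alone would be misled.

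Most of this stands, and it limits the point. It does not remove it. The ADA section does not itself promise a by-visit table, marginal counts do not show within-patient change, and listings keep the data without fixing the rules for classifying it.

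Three stronger readings are tempting, and the documents do not support them:

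- A reader might infer that the immunogenicity rate is overstated. The SAP defines no overall rate and the documents give no prevalence of pre-existing reactivity, so overstatement is possible but not shown.
- A reader might infer that the analysis against PK, efficacy and safety will use a misclassified variable. That exploration is optional and specifies no variable.
- A reader might infer that a dose pattern will be created or hidden. Only descriptive summaries are planned, and one patient weighs as heavily in any binary outcome in cohorts of this size.

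Finally, the protocol text available is essentially the synopsis and schedule, so an ADA definition elsewhere in the protocol cannot be excluded.

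**Conclusion.** The point holds as a gap in definition. As written, SAP 9.7.1.7.2 does not yield a measure of drug-induced immunogenicity, although the sample needed for one is collected from every patient and the objective calls for it. A post-dose positive count can include pre-existing reactivity, and boosted and flat responses fall in the same category.

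The size is conditional. Each patient reactive before and after dosing without a boost accounts for 33, 17 or 12.5 percentage points of the post-dose positive proportion in a cohort of 3, 6 or 8. At an assumed prevalence of 5% or 10%, the chance of at least one patient reactive pre-dose among 25 is 0.72 or 0.93. At zero prevalence the effect is nil. Inability to separate a boosted from a flat response likewise matters only if some patients are reactive pre-dose. The change is worth making before analysis, but the listings mean that nothing is irrecoverable.

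**What to change.** In SAP 9.7.1.7.2, classify each patient against the pre-dose sample:

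- **Treatment-induced:** negative pre-dose and positive at any post-dose visit.
- **Treatment-boosted:** positive pre-dose, with a titer rise of at least a multiple pre-specified from assay precision. The documents give neither a multiple nor the precision, so the sponsor must supply it from the assay's validation.
- **Pre-existing, unaffected:** positive pre-dose without such a rise.
- **Negative:** negative pre-dose and at all post-dose visits.

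Report treatment-emergent ADA (induced plus boosted) by cohort, over patients with a pre-dose and at least one post-dose result. Report pre-dose prevalence separately. State how inconclusive or missing pre-dose results are handled. Use this classification in any exploration against PK, efficacy or safety.

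The cost is SAP wording and one derived variable; no new samples are needed. The reported figure may move either way: removing unaffected pre-existing reactors lowers it, while counting a positive at any post-dose visit can raise it above a single-visit percentage.

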9.7.2. Determination of Sample Size

A sample size of 3-8 patients for each cohort is not based on formal power considerations. The table below defines the probability of observing at least one patient with a DLT or SAE among 3, 6, or 8 patients for assumed probabilities of a DLT or SAE (see Table 2).

Table 2: Probabilities of DLT or SAE

Probability of a DLT/SAE	Probability of Observing ≥ 1 Patient with DLT/SAE		
	Cohort of 3 Patients	Cohort of 6 Patients	Cohort of 8 Patients
0.05	0.143	0.265	0.337
0.1	0.271	0.469	0.57
0.15	0.386	0.623	0.728
0.2	0.488	0.738	0.832
0.25	0.578	0.822	0.9
0.3	0.657	0.882	0.942
0.35	0.725	0.925	0.968

0.4	0.784	0.953	0.983
-----	-------	-------	-------

9.8. CHANGES IN THE CONDUCT OF THE STUDY OR PLANNED ANALYSES

9.8.1. Protocol Amendments

-

Amendment 1 made the following changes:

- Sponsor address;
- Exclusion criteria 19f.

Amendment 2 made the following changes:

- The additional collection of safety assessments the next day after dosing;
- The addition of a 24-hour post-dose PK sample for Cohorts 3 and 4;
- Clarification on timing and specificity of some assessments.

Amendment 3 made the following changes:

- Changed the dose of Cohort 4 to 4mg (0.1 mL);
- Updated CST trigger for rescue medication;
- Added 14-day extension to screening window;
- Updated safety data and margin;
- Updated inclusion criteria;
- Updated schedule of activities;
- Updated prohibited medications;
- Updated storage conditions.

APPENDIX I: SCHEDULE OF ASSESSMENTS

Table 3: Schedule of Assessments

Activity/Assessment	Screening Baseline ^a	Visit 1	Visit 2	Visit 3	Visit 4	Visit 5	Visit 6	Visit 7	Visit 8	Visit 9
Visit Day ± Window	Day -30 to -2 ^c	Day 1	Day 2	Day 8 ± 2	Day 28± 5	Day 56± 5	Day 84± 5	Day 112 ± 5	Day 140 ± 5	Day 168 ± 5
Informed Consent	X									
Inclusion/Exclusion Review	X									
Demographics	X									
Medical and Drug History	X									
Concomitant Medication	X	X	X	X	X	X	X	X	X	X
Concurrent Procedures	X	X	X	X	X	X	X	X	X	X
Electrocardiogram (ECG) (12-lead)	X				X					X
Vital Signs ^d	X	X	X	X	X	X	X	X	X	X
Physical Examination	X									
Clinical Lab Tests ^e	X				X			X		X
Pregnancy test ^f		X								
BCVA (ETDRS) ^g	OU	OU	OU	OU	OU	OU	OU	OU	OU	X
IOP ^h	OU	OU	OU	OU	OU	OU	OU	OU	OU	OU
Color Fundus Photos (7-field) ⁱ	OU	OU	OU	OU	OU	SE				OU
SD-OCT ^j	OU	OU	OU	OU	OU	OU	OU	OU	OU	OU
OCT-A ^{i,j}		OU				SE				SE
Biomicroscopy	OU	OU	OU	OU	OU	OU	OU	OU	OU	OU
Ophthalmoscopy ^k	OU	OU	OU	OU	OU	OU	OU	OU	OU	OU
Prednisolone acetate 1% ^l	X									
Dispense ^l										
AG-73305 Dosing ^m		SE								

Activity/Assessment	Screening	Visit 1		Visit 2		Visit 3		Visit 4		Visit 5		Visit 6		Visit 7		Visit 8		Visit 9	
		Baseline ^a	Next Day Follow-up ^b	Week 1	Week 4	Week 8	Week 12	Week 16	Week 20	Week 24 or Early Term									
Adverse Events		X	X	X	X	X	X	X	X	X	X	X	X	X	X	X	X	X	
Plasma Drug Monitoring ⁿ		X	X	X	X	X	X	X	X	X	X	X	X	X	X	X	X	X	
Immunogenicity ^o		X	X	X	X	X	X	X	X	X	X	X	X	X	X	X	X	X	

Abbreviations: BCVA = best-corrected visual acuity; ECG = electrocardiogram; ETDRS = Early Treatment of Diabetic Retinopathy Study; IOP = intraocular pressure; OU = both eyes; SD-OCT = spectral domain optical coherence tomography; OCT-A = OCT angiography; SE = study eye

- a. Preferably within Monday-Thursday to ensure next day safety assessment and timely collection of 24-hour post dose plasma drug monitoring sample. Any Baseline planned on a Friday needs to be pre-approved by Allgenesis
- b. Patients who do not provide PK sample may complete the safety follow-up within 1-3 days post dose
- c. An additional 14-day extension to the 30-day screening window is allowed, upon approval from Sponsor and Medical Monitor, on a case-by-case basis
- d. Blood pressure, heart rate, body temperature, and respiratory rate
- e. Blood chemistries, hematology and urinalysis and drugs of abuse screen (Screening only)
- f. Urine pregnancy test, females of childbearing potential only
